## **11.0 STUDY PROCEDURES**

### **11.1 Duration of study**

Subjects will be enrolled over 48 months, so the total study duration is expected to be 64 months, including the determination of SEB (surrogate end-point biomarkers), statistical analysis and drafting of the final report.

The study is considered concluded when the last enrolled subject has completed the follow-up visit one year after the end of the experimental treatment.

### **11.2 Screening**

Within the month preceding randomization, the following must be guaranteed:

- signature of written informed consent;
- eligibility verification: evaluation of inclusion/exclusion criteria.
- blood tests and/or instrumental tests;
- colonoscopy with evaluation of the presence of adenomatous polyp  $\geq 1$  cm and collection of biopsy material necessary for tissue determinations.

### **11.3 Baseline Visit**

- Clinical visit and detection of vital parameters: weight, height, blood pressure (BP), Performance status (PS) according to ECOG;
- Blood sampling for the determination of circulating biomarkers and for the determination of plasma absorption of the active ingredients present in the botanical extracts at time zero (only for patients enrolled at the EO Ospedali Galliera).
- Delivery of the food diary.
- Anamnesis, concomitant pathologies and family history (I and II degree) for CRC/other neoplasms;
- Concomitant therapies;
- Randomization;
- Delivery of supplement/placebo: a package containing sufficient supplement for a six-week administration period + 6 spare tablets (90 tablets) will be delivered. The kit must be returned at the end of the study visit.

### **11.4 Final Visit (after 4-6 weeks of treatment)**

- Clinical visit and detection of vital parameters: weight, BP, PS according to ECOG;

- Blood sampling for the determination of circulating biomarkers.
- Blood sampling to determine the plasma absorption of the active ingredients present in the botanical extracts, before and 1 hour after the last treatment (Only for patients enrolled at the EO Ospedali Galliera);
- Concomitant therapies;
- Adverse events and symptoms;
- Patient kit return and compliance assessment;
- Food diary collection and evaluation;
- Polypectomy and biopsy for tissue determinations, to be carried out after 2-5 hours of taking the last dose.

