### **10.2 Dosage groups, duration of exposure and dose selection**

Subjects will take blueberry extract (Mirtoselect®) 1 g/daily divided into 2 daily administrations of 500 mg or placebo A, together with turmeric extract (Meriva®) 1 g/daily divided into 2 daily administrations of 500 mg or placebo B for a minimum period of 4 weeks and a maximum period of 6 weeks.

Mirtoselect® 500 mg, Meriva® 500 mg, placebo A or B tablets will be packaged in blisters of 9 tablets each. The intake of the supplement or placebo will be in the order of 2 tablets per day of each supplement or respective placebo to be taken in the morning and evening always at the same time.

The choice of a daily dose of 1 g of blueberry extract is based on a large literature regarding previous studies that ensure its safety even at doses much higher than 1 g. In particular, with blueberry extract the results on efficacy, pharmacokinetics and safety of several clinical studies are available starting from the dose of 160 mg with 2 daily administrations, up to the daily dose of 10.8 g for 7 days of treatment (27-29).

The choice of a daily dose of 1 g of curcumin extract is based on previous studies demonstrating that the complexation of curcumin with phosphatidylcholine is able to increase the bioavailability of the active ingredient (21,22), and this allows to lower the doses compared to previous studies with non-complexed curcumin (20). In fact, the supplement based on curcumin extract and phospholipid in a 1:2 ratio has demonstrated efficacy in the treatment of osteoarthritis and anterior uveitis (30,31) due to its pharmacokinetic characteristics and in particular for its combination with the phospholipid part which allows to overcome some limits of the oral preparations of curcumin, such as instability at intestinal pH values, low solubility in water, poor oral bioavailability and rapid conjugation and excretion. Furthermore, the curcumin extract has proven to be safe and well tolerated. Oral intake in the clinical studies has never been associated with significant side effects.

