#### **11.5 Follow-up (1 year after the end of treatment)**

The follow-up visit, 1 year after the end of treatment, must be performed one year  $\pm$  1 month after the end-of-study visit.

During the visit the following data must be collected:

- Clinical visit and detection of vital parameters: weight, BP, PS according to ECOG;
- Adverse events and symptoms;
- CCR onset (histological evaluation/colonoscopy/polypectomies);
- Relevant clinical notes.

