### **11.9 Food diary**

A food diary will be provided to the patient at the beginning of the study and must be filled out daily by the patient. The diary is intended to monitor the intake of foods consumed by the subject in treatment and their possible interaction with the compounds. The diary, like the CRF, must be forwarded to the coordinating center 5 working days after the end-of-study visit.

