## 12.0 FLOW CHART

Exam/Procedure	Screening	Baseline Visit	Final Visit	Follow up
Written Informed Consent	X			
Colonoscopy/identification of polyp >1 cm (histology)	X			
Blood tests 	X			
Check eligibility	X			
Randomization		X		
Clinical Visit 		X	X	X
Control colonoscopy (according to clinical practice)				X
Anamnesis/clinical history/family history for CRC		X		
Biomarker sampling		X	X 	
Pharmacokinetic sampling		X	X 	
Polypectomy and Tissue Collection for Biomarker 		X	X	
Compliance			X	
Adverse reactions/adverse events			X	X
Concomitant treatment		X	X	X

**1** Routine tests required for colonoscopy.

**2** Evaluation of vital parameters: weight, height, BP, PS ECOG.

**3** Post-dose sampling.

**4** To determine the absorption of the active ingredients, a sample will be taken before and 1 hour after taking the last dose of treatment.

**5** Polypectomy to be performed within 2-5 hours of taking the last dose of treatment.

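### Non-serious on-treatment adverse events rest on 4 to 6 weeks of recall, although the patient already keeps a daily diary that could record them cheaply

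*Combined protocol and SAP*

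**What the plan says.** Section 11.4 (Final Visit) lists "Adverse events and symptoms" among its procedures, and section 11.5 lists the same item for the one-year follow-up. The flow chart in section 12.0 agrees: its row "Adverse reactions/adverse events" is marked under Final Visit and Follow up only, and it has no column between Baseline Visit and Final Visit.

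Section 10.2 sets the length of treatment: "for a minimum period of 4 weeks and a maximum period of 6 weeks". At the end of it, section 11.4 places the resection at the same visit: "Polypectomy and biopsy for tissue determinations, to be carried out after 2-5 hours of taking the last dose". The next scheduled contact is fixed in section 11.5: "The follow-up visit, 1 year after the end of treatment, must be performed one year" (with a margin of one month) after the end-of-study visit.

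The patient receives a diary at baseline, and section 11.9 says it "must be filled out daily by the patient". Its stated purpose is to follow foods and their possible interaction with the study products; no symptom entry is mentioned. Section 11.4 has it collected and evaluated at the Final Visit.

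Two parts of the plan use the adverse event data. Section 9.2 makes tolerability a secondary objective. Section 17.2 makes the number of adverse events one of two endpoints of an interim harm analysis, held when about half the patients have completed treatment.

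**The concern.** No visit, call or symptom record is planned between handing over the kit and the Final Visit. A short-lived event in week 1, such as a few days of nausea, enters the data only if the patient volunteers it or still remembers it weeks later. For a food supplement, such mild events are much of what a tolerability objective measures.

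Two results are exposed. The tolerability summary may under-count mild events and would lack reliable onset and duration. The interim adverse event comparison loses power, because equal under-recording in both arms shrinks the absolute difference between them. That look has 50 patients and is sized only for a difference of 40 percentage points, so it has little margin.

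The loss is avoidable, since the patient is already writing in a study document every day.

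**Working it through.** **1. Is there another route by which events are asked about earlier?**

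- Section 14.1 provides for periodic telephone monitoring, but its purpose is to check entries in the case report form. It is not a call to patients.
- Section 16.2 requires every adverse event to be recorded and serious ones to be notified within 24 hours, counted from when the investigator first learns of them. It provides a route for events that become known but schedules no enquiry.
- Section 15.1 names an adverse event as a possible reason for leaving early, so an event that ends treatment would normally come to light.

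What remains exposed is the non-serious, transient event that the patient does not report unprompted.

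**2. Recall windows**

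- On treatment: 4 × 7 = 28 days to 6 × 7 = 42 days.
- After the Final Visit: 365 ± 30 days, about 335 to 395 days.

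The interim look uses the first window. The second applies to events after the Final Visit, so it bears on the tolerability objective and hardly on the interim.

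**3. The plan's own interim statement**

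Section 17.2 says 50 patients suffice to detect an absolute difference of 40 points in adverse event frequency. It gives no control rate, significance level or numerical power. I assume 25 per arm, Fisher's exact test (named in section 17.3 for adverse events) and a two-sided 5% level (stated in section 17.1 for the primary endpoint only). Exact power is the sum, over all pairs of counts (i, j), of

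Bin(i; 25, p₁) × Bin(j; 25, p₂) × 1[Fisher p ≤ 0.05].

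| True rates | Power |
|---|---|
| 5% vs 45% | 90% |
| 10% vs 50% | 83% |
| 20% vs 60% | 79% |
| 30% vs 70% | 78% |

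The plan's statement is plausible, and I do not dispute it.

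**4. Effect of incomplete capture**

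Let s be the share of affected patients who are recorded, equal in both arms. The observed rates are s·p₁ and s·p₂, and the observed difference is s × 40 points. The documents give no value for s, so these are assumed values.

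| s | Observed, true 10% vs 50% | Difference | Power | Power, true 20% vs 60% |
|---|---|---|---|---|
| 1.0 | 10% vs 50% | 40 | 83% | 79% |
| 0.9 | 9% vs 45% | 36 | 76% | 69% |
| 0.8 | 8% vs 40% | 32 | 68% | 58% |
| 0.5 | 5% vs 25% | 20 | 37% | 31% |

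The 50% row is severe: an affected patient goes unrecorded only if every event that patient had is missed.

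**The case against.** The strongest reply is that nothing here is an error. Sections 11.4 and 11.5 and the flow chart agree with one another, the course is short, the products are food supplements, and serious or treatment-ending events have their own routes. All of that stands. It makes this an improvement to offer, not a defect that undermines the trial.

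A reader might also infer more than the documents support:

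- *That the whole interim harm look rests on long recall.* It does not. Adenoma size, the other endpoint, does not depend on recall, and the year-long gap falls after the point at which the interim compares the arms.
- *That recall loss favours one arm.* Under blinding, forgetting should be similar in both arms. The cost is under-counting and power.
- *That longer exposure than in earlier bilberry studies makes the gap worse.* Section 10.2 cites experience "up to the daily dose of 10.8 g for 7 days of treatment", but this trial gives 1 g a day. Comparing duration while ignoring a dose 10.8 times lower is not a fair argument, and the durations of the other cited bilberry studies are not given.
- *That symptoms of the procedure contaminate the report.* Section 11.4 lists adverse events before the polypectomy and fixes no order within the visit, so this is conjecture.
- *That power falls to 37%.* That is one assumed value of s. At 90% capture the loss is about 7 points.

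**Conclusion.** The point holds as a cheap improvement, limited to non-serious, transient events during treatment. The plan first asks about them after 28 to 42 days, and its daily diary is not used for them. The result is probable under-counting for the tolerability objective and reduced power for the interim adverse event comparison.

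The extent is unknown. From 83% at full capture, power falls by about 7 points at 90% capture and 15 points at 80%. This assumes 25 per arm, a two-sided Fisher test at 5%, true rates of 10% and 50%, and equal capture in both arms. The primary β-catenin analysis is not affected.

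**What to change.** - In section 11.9, add a daily symptom line to the existing diary: symptom, start, stop, severity.
- In section 11.4, require the investigator to take adverse events from the diary at the Final Visit, in the same way for every patient in both arms. The diary is already collected and evaluated at that visit.

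The cost is a reprinted diary page and a line in the case report form. The downsides are slightly more burden for patients and more minor events to process. No endpoint, sample size or visit changes.

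A telephone check of adverse events some weeks after the last dose would shorten the year-long gap for later events. It is an extra contact, is optional, and is not needed for the diary change to work.

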#### **11.5 Follow-up (1 year after the end of treatment)**

The follow-up visit, 1 year after the end of treatment, must be performed one year  $\pm$  1 month after the end-of-study visit.

During the visit the following data must be collected:

- Clinical visit and detection of vital parameters: weight, BP, PS according to ECOG;
- Adverse events and symptoms;
- CCR onset (histological evaluation/colonoscopy/polypectomies);
- Relevant clinical notes.

#### **11.6 Compliance**

To manage the study supplements accountability, a balance sheet will be drawn up to maintain traceability of the inventory of products, shipping receipts and the kit administration. This register will be updated regularly and, for each shipment, will identify the subject number, the randomization number and the quantity of supplements shipped. The accountability form will be stored/used in all the places where the supplements will be stored for subsequent delivery to patients, the main pharmacy, the pharmacies of the individual centers, the clinical unit and other delivery locations. The form will include, in addition to the delivery register, all other possible operations for the management of the supplements (receipts, transfers, returns, damaged packages). The register form will be provided by the coordinating center to the participating sites.

### **11.7 Collection and management of biological material**

Tissue samples collected during colonoscopies for immunohistochemical determinations will be collected centrally at SC Anatomia Patologica, EO Ospedali Galliera, upon specific request of the coordinating center and at the end of the study (within the month after the last enrolled patient took the last dose of treatment). Transparent labeled envelopes will be provided to the enrolling centers. The labels will contain: name of the study, center number, randomization number and patient registration, date of the exam and time (1=baseline, 2=final).

Blood samples for circulating biomarkers will be collected centrally by the Lab Analysis of the Prevention and Oncology Genetics Division of the IEO in Milan upon specific request and in any case at the end of the study (within the month after the last enrolled patient took the last dose of treatment). In both cases, guides for biological samples collection, preparation, storage and shipment to the appropriate centralized center will be provided.

Blood samples for the determination of plasma absorption of the active ingredients will be performed only on the group of patients enrolled at the Gastroenterology unit of the coordinating center, at EO Ospedali Galliera and will be analyzed by an external laboratory. A guide will be provided for samples collection, preparation, storage times and shipment to the centralized collection center.

### **11.8 Concomitant treatment**

During the study, the intake of Indian foods is not recommended, as is the intake of H2 blockers (cimetidine, ranitidine, nizatidine, famotidine) and proton pump inhibitors (omeprazole, esomeprazole, rabeprazole, pantoprazole, lansoprazole).

If the subject uses antacids and/or lactic ferments, he/she will be instructed to take them at least 2 hours before or after the experimental treatment.

The investigator must detail in the CRF any intake of the above-described substances and any other concomitant drugs or food supplements.

### **11.9 Food diary**

A food diary will be provided to the patient at the beginning of the study and must be filled out daily by the patient. The diary is intended to monitor the intake of foods consumed by the subject in treatment and their possible interaction with the compounds. The diary, like the CRF, must be forwarded to the coordinating center 5 working days after the end-of-study visit.

## 12.0 FLOW CHART

Exam/Procedure	Screening	Baseline Visit	Final Visit	Follow up
Written Informed Consent	X			
Colonoscopy/identification of polyp >1 cm (histology)	X			
Blood tests 	X			
Check eligibility	X			
Randomization		X		
Clinical Visit 		X	X	X
Control colonoscopy (according to clinical practice)				X
Anamnesis/clinical history/family history for CRC		X		
Biomarker sampling		X	X 	
Pharmacokinetic sampling		X	X 	
Polypectomy and Tissue Collection for Biomarker 		X	X	
Compliance			X	
Adverse reactions/adverse events			X	X
Concomitant treatment		X	X	X

**1** Routine tests required for colonoscopy.

**2** Evaluation of vital parameters: weight, height, BP, PS ECOG.

**3** Post-dose sampling.

**4** To determine the absorption of the active ingredients, a sample will be taken before and 1 hour after taking the last dose of treatment.

**5** Polypectomy to be performed within 2-5 hours of taking the last dose of treatment.

## **13.0        ETHICAL ASPECTS**

This protocol complies with the principles established by the 18th World Medical Assembly in Helsinki, 1964 and subsequent amendments/additions and with Good Clinical Practice.

### **13.1        Informed consent**

The investigator must explain to each patient (or legal representative) the nature of the study, its purpose, procedures, expected duration, potential risks and benefits and any adverse events or reactions that may occur. Each patient must be informed that participation in the study is voluntary and that he/she may withdraw from it at any time, withdrawal of consent will not affect his/her subsequent clinical treatment or relationship with the physician. The informed consent will be prepared by the coordinating center by means of a standard written statement, using non-technical language. The patient must demonstrate that he/she has understood the information contained in the consent, by signing and dating it; he/she must also be provided with a copy of the document. If the patient is unable to read or sign the document, the oral and written presentation of the study may be provided to his/her legal representative who can sign and date the document. No patient may be enrolled in the study before his/her informed consent has been obtained. An original signed copy of the patient's written informed consent must be kept in the appropriate section of the Investigator's File of the enrolling center.

### **13.2        Patient safety**

Patient names will not be recorded, but each subject will be identified with a treatment number (randomization number) and a registration number. These numbers will identify the patient and must be included in all CRFs. In order to avoid misidentification, the date of birth must be reported in the CRFs to identify the subjects themselves. The investigators guarantee that all persons involved in this study will respect the confidentiality of any information regarding the subject participating in the trial. All parties involved in this clinical trial will maintain the utmost confidentiality to ensure that neither the person nor the privacy of the patient participant's family is violated; adequate measures will be taken to prevent unauthorized persons from accessing the study data. The processing of personal data of patients participating in the trial, and in particular the related data regarding consent, will be in accordance with local privacy laws:

Legislative Decree 196/03 and subsequent amendments (“Privacy Code”), “Guidelines for the processing of personal data in the context of clinical trials of medicinal products” with particular reference to the profiles relating to the methods of data processing, data requirements, the designation of Managers and Persons in Charge and the custody and security of information.

## **14.0 DATA COLLECTION AND MONITORING PLAN**

### **14.1 Data collection and monitoring procedures**

Study data will be collected via a paper CRF that must be faxed to the coordinating center. CRFs must be sent within 5 working days of the visits. Checks on the receipt of CRFs will be carried out by the Coordinating center on a regular basis during the study.

Monitoring will be carried out according to this plan:

- opening of the center by teleconference (SIV) and concomitant shipment of supplements
- visit to the center after approximately 6 months ( $\pm$  one month) from the inclusion of the first patient
- closing visit of the center at the end of the study.

Periodic telephone monitoring will be carried out to verify the correct entry of data into the CRF.

It is the responsibility of the participating site investigator to prepare and maintain adequate and accurate CRFs for each subject enrolled in the study. All CRFs must be completed to ensure accurate interpretation of the data, a black ballpoint pen must be used to ensure clarity of the data transcription on the CRF. If a correction is necessary, the information that needs to be changed must not be overwritten. The corrected information must be transcribed next to the previous value with the reason for the correction, initialed and dated by the authorized person.

### **14.2 Quality Assurance**

The researchers of the participating centers, will have to guarantee the quality of the data, each information reported on the CRF will be systematically verified for coherence, completeness and correctness by the Coordinating Center that may ask for clarifications in case of doubtful data. Local quality controls will be carried out by the coordinating center as responsible for the monitoring plan.

### **14.3 Source documents**

The source data must be stored and recorded in a hospital medical record; if such records for outpatient subjects are not provided for by the practice of the facility or clinic where the trial is being conducted, they must be prepared for the purposes of the legislation on clinical trials of medicinal products. If paper CRFs are used as source documents, the principal investigator of

the center must declare the methods of archiving such source documents and, after having signed, stamped and dated them, insert the same CRFs into the outpatient record as an integral part of the same.

At the end of the trial, the documents must be kept at the center for a period of 10 years. If the responsible investigator changes workplace, he must forward the name of a new trial manager to the coordinating center.

